Appendix A: Total Bilirubin Table for Term and Preterm Neonates

PARAMETER	GRADE 1 MILD	GRADE 2 MODERATE	GRADE 3 SEVERE	GRADE 4 POTENTIALLY LIFE- THREATENING
Total Bilirubin ¹⁸ , High (mg/dL; $\mu\text{mol/L}$) ¹⁹ Term Neonate ²⁰ < 24 hours of age	4 to < 7 68.4 to < 119.7	7 to < 10 119.7 to < 171	10 to < 17 171 to < 290.7	≥ 17 ≥ 290.7
24 to < 48 hours of age	5 to < 8 85.5 to < 136.8	8 to < 12 136.8 to < 205.2	12 to < 19 205.2 to < 324.9	≥ 19 ≥ 324.9

PARAMETER	GRADE 1 MILD	GRADE 2 MODERATE	GRADE 3 SEVERE	GRADE 4 POTENTIALLY LIFE- THREATENING
48 to < 72 hours of age	8.5 to < 13 145.35 to < 222.3	13 to < 15 222.3 to < 256.5	15 to < 22 256.5 to < 376.2	≥ 22 ≥ 376.2
72 hours to < 7 days of age	11 to < 16 188.1 to < 273.6	16 to < 18 273.6 to < 307.8	18 to < 24 307.8 to < 410.4	≥ 24 ≥ 410.4
7 to 28 days of age (breast feeding)	5 to < 10 85.5 to < 171	10 to < 20 171 to < 342	20 to < 25 342 to < 427.5	≥ 25 ≥ 427.5
7 to 28 days of age (not breast feeding)	1.1 to < 1.6 x ULN	1.6 to < 2.6 x ULN	2.6 to < 5.0 x ULN	≥ 5.0 x ULN
Preterm Neonate²⁰ 35 to < 37 weeks gestational age	Same as for Total Bilirubin, High, Term Neonate (based on days of age).	Same as for Total Bilirubin, High, Term Neonate (based on days of age).	Same as for Total Bilirubin, High, Term Neonate (based on days of age).	Same as for Total Bilirubin, High, Term Neonate (based on days of age).
32 to < 35 weeks gestational age and < 7 days of age	NA	NA	10 to < 14 171 to < 239.4	≥ 14 ≥ 239.4
28 to < 32 weeks gestational age and < 7 days of age	NA	NA	6 to < 10 102.6 to < 171	≥ 10 ≥ 171
< 28 weeks gestational age and < 7 days of age	NA	NA	5 to < 8 85.5 to < 136.8	≥ 8 ≥ 136.8
7 to 28 days of age (breast feeding)	5 to < 10 85.5 to < 171	10 to < 20 171 to < 342	20 to < 25 342 to < 427.5	≥ 25 ≥ 427.5
7 to 28 days of age (not breast feeding)	1.1 to < 1.6 x ULN	1.6 to < 2.6 x ULN	2.6 to < 5.0 x ULN	≥ 5.0 x ULN

¹⁸ Severity grading for total bilirubin in neonates is complex because of rapidly changing total bilirubin normal ranges in the first week of life followed by the benign phenomenon of breast milk jaundice after the first week of life. Severity grading in this appendix corresponds approximately to cut-offs for indications for phototherapy at grade 3 and for exchange transfusion at grade 4.

¹⁹ A laboratory value of 1 mg/dL is equivalent to 17.1 $\mu\text{mol/L}$.

²⁰ Definitions: Term is defined as ≥ 37 weeks gestational age; near-term, as ≥ 35 weeks gestational age; preterm, as < 35 weeks gestational age; and neonate, as 0 to 28 days of age.

Reference

U.S. Department of Health and Human Services, National Institutes of Health, National Institute of Allergy and Infectious Diseases, Division of AIDS. Division of AIDS (DAIDS) Table for Grading the Severity of Adult and Pediatric Adverse Events, Version 2.1. [March 2017]. Available from: <https://rsc.tech-res.com/docs/default-source/safety/daids-ae-grading-table-mar2017.pdf> (accessed 26 May 2017).

12.8. Appendix 8: Toxicity Management

ANEMIA

Grade 1 (mild) hemoglobin decrease:

Any hemoglobin decrease meeting the definition of Grade 1 must be repeated with the following additional tests:

1. peripheral blood smear
2. indirect bilirubin (abnormal if increased >50% from baseline)
3. haptoglobin (abnormal if ≤ 25 mg/dL)
4. reticulocyte count (abnormal if $\geq 4\%$)

If the additional tests are within the normal range, participants may continue study medication. If one or more of the additional tests is abnormal or suggestive of hemolytic anemia as specified above, participants will permanently discontinue study medication and be withdrawn from the trial. Participants should be followed up until resolution of anemia.

Grade 2 (moderate) hemoglobin decrease:

Any hemoglobin decrease meeting the definition of Grade 2 must be repeated with the following additional tests:

1. peripheral blood smear
2. indirect bilirubin (abnormal if increased > 50% from baseline)
3. haptoglobin (abnormal if ≤ 25 mg/dL)
4. reticulocyte count (abnormal if $\geq 4\%$)

If the additional tests are within the normal range, participants may continue study medication. If one or more of the additional tests is abnormal or suggestive of hemolytic anemia as specified above, participants will permanently discontinue study medication and be withdrawn from the trial. Consultation with a Hematologist should be considered. Participants should be followed up until resolution of anemia.

Grade 3 (severe) or Grade 4 (potentially life threatening) hemoglobin decrease:

Any hemoglobin decrease meeting the definition of Grade 3 or 4 must be repeated with the following additional tests:

1. peripheral blood smear
2. indirect bilirubin
3. haptoglobin
4. reticulocyte count

Participants will permanently discontinue study medication and be withdrawn from the trial. Consultation with a Hematologist should be considered. Participants should be followed up until resolution of anemia.

TOTAL BILIRUBIN ELEVATION

Grade 1 (mild) bilirubin elevation (1.1 - 1.5 times ULN) or Grade 2 (moderate - 1.6-2.5 times ULN):

Any bilirubin value above the upper limit of normal must be repeated and fractionated (direct and indirect bilirubin). Participants may continue study medication. Participants should be followed up until resolution (return to baseline) of elevation.

Grade 3 (severe – 2.6-5.0 times ULN) or 4 (life-threatening - > 5.0 times ULN) bilirubin elevation:

Any bilirubin value above the upper limit of normal must be repeated and fractionated (direct and indirect bilirubin). Participants will permanently discontinue study medication and be withdrawn from the trial. Participants should be followed up until resolution (return to baseline) of bilirubin elevation.

AST AND ALT ELEVATION

See Section [12.6](#).

RASH

Grade 1 rash (Localized macular rash):

Participants with Grade 1 rash should be evaluated by the Investigator immediately. A dermatologist may be consulted and a biopsy may be obtained if recommended by the dermatologist. The study drug should be permanently discontinued if the following signs or symptoms are noted at any time:

1. Temperature >38.5°C
2. Lymphadenopathy
3. Pharyngitis
4. Any indication of internal organ involvement (hepatitis, nephritis)

In the absence of the above signs or symptoms, participants with Grade 1 rash may continue the study drug at the discretion of the Investigator. The participant should be advised to contact the Investigator immediately if there is any worsening of the rash, if any systemic signs or symptoms worsen, or if mucosal ulceration develops. If the rash is considered to be most likely due to concomitant illness or non-study medication, standard management, including discontinuation of the likely causative agent, should be undertaken. If no other causative factor is found after clinical evaluation, the participant may be treated symptomatically until the rash resolves. Antihistamines, topical corticosteroids or antipruritic agents may be prescribed. The participant should remain on the study to be followed for safety and PK as outlined in Section [2](#).

Grade 2 rash (Diffuse macular, maculopapular, or morbilliform rash OR Target lesions):

Participants with Grade 2 rash should be evaluated by the Investigator immediately. Digital photographs should be obtained. A dermatologist may be consulted and a biopsy may be obtained if recommended by the dermatologist. The study drug should be permanently discontinued if the following signs or symptoms are noted at any time:

- Temperature > 38.5°C
- Lymphadenopathy
- Pharyngitis
- Any indication of internal organ involvement (hepatitis, nephritis)

In the absence of the above signs or symptoms, participants with Grade 2 rash may continue the study drug at the discretion of the Investigator. It should be noted that oral mucosal **erosions** may be part of a Grade 2 rash. Any mucosal **ulceration** increases the severity of the rash to at least Grade 3. The participant should be advised to contact the Investigator immediately if there is any worsening of the rash, if any systemic signs or symptoms worsen, or if mucosal ulceration develops. If the rash is considered to be most likely due to concomitant illness or non-study medication, standard management, including discontinuation of the likely causative agent, should be undertaken. If no other causative factor is found after clinical evaluation, the participant may be treated symptomatically until the rash resolves. Antihistamines, topical corticosteroids or antipruritic agents may be prescribed. The participant should remain on the study to be followed for safety and PK as outlined in Section 2.

Grade 3 rash (Diffuse macular, maculopapular, or morbilliform rash with vesicles or limited number of bullae OR Superficial ulcerations of mucous membrane limited to one site):

Participants with a Grade 3 rash will permanently discontinue the study medication. The participant should be evaluated in the physician's office immediately and should be seen in the physician's office or contacted by phone every 2 days until the rash resolves. A dermatologist should be consulted and digital photographs and a biopsy should be obtained. Antihistamines, topical corticosteroids or antipruritic agents may be prescribed at the discretion of the Investigator. The participant should be advised to contact the Investigator immediately if there is any worsening of the rash, if any systemic signs or symptoms appear, or if mucosal involvement develops. The participant should remain on the study to be followed for safety and PK as outlined in Section 2.

Grade 4 rash (Extensive or generalized bullous lesions OR Stevens-Johnson syndrome OR Ulceration of mucous membrane involving two or more distinct mucosal sites OR Toxic epidermal necrolysis (TEN)):

Participants with a Grade 4 rash will permanently discontinue the study medication. A dermatologist should be consulted and digital photographs and a biopsy should be obtained. Sponsor and PPD Medical Monitor should be notified of this serious adverse event within 24hr via phone or fax. The participant should be closely followed everyday until resolution of the reaction. The participant should remain on the study to be followed for safety and PK as outlined in Section 2.

ALLERGIC REACTION

Grade 1 allergic reaction (Pruritis without rash):

Participants with Grade 1 allergic reaction should be evaluated by the Investigator immediately. The study drug should be permanently discontinued if the following signs or symptoms are noted at any time:

1. Temperature > 38.5°C
2. Eosinophilia
3. Respiratory involvement including bronchospasm, laryngospasm, or angioedema
4. Any indication of internal organ involvement (hepatitis, nephritis)

In the absence of the above signs or symptoms, participants with Grade 1 allergic reaction may continue the study drug at the discretion of the Investigator. The participant should be advised to contact the Investigator immediately if there is any worsening of the allergic reaction and/or if any systemic signs or symptoms worsen. If the allergic reaction is considered to be most likely due to concomitant illness or non-study medication, standard management, including discontinuation of the likely causative agent, should be undertaken. If no other causative factor is found after clinical evaluation, the participant may be treated symptomatically until the rash resolves. Antihistamines, topical corticosteroids or antipruritic agents may be prescribed. The participant should remain on the study to be followed for safety and PK as outlined in Section 2.

Grade 2 allergic reaction (Localized urticaria):

Participants with Grade 2 allergic reaction should be evaluated by the Investigator immediately. The study drug should be permanently discontinued if the following signs or symptoms are noted at any time:

1. Temperature > 38.5°C
2. Eosinophilia
3. Respiratory involvement including bronchospasm, laryngospasm, or angioedema
4. Any indication of internal organ involvement (hepatitis, nephritis)

In the absence of the above signs or symptoms, participants with Grade 2 allergic reaction may continue the study drug at the discretion of the Investigator. The participant should be advised to contact the Investigator immediately if there is any worsening of the allergic reaction and/or if any systemic signs or symptoms worsen. If the allergic reaction is considered to be most likely due to concomitant illness or non-study medication, standard management, including discontinuation of the likely causative agent, should be undertaken. If no other causative factor is found after clinical evaluation, the participant may be treated symptomatically until the rash resolves. Antihistamines, topical corticosteroids or antipruritic agents may be prescribed. The participant should remain on the study to be followed for safety and PK as outlined in Section 2.

Grade 3 allergic reaction (Generalized urticaria or angioedema):

Participants will permanently discontinue the study medication and be withdrawn from the trial. Participants will be treated as clinically appropriate. Participants should be followed up until resolution of the adverse event and standard management should be undertaken.

Grade 4 allergic reaction (Anaphylaxis):

Participants will permanently discontinue the study medication and be withdrawn from the trial. Participants will be treated as clinically appropriate. Participants should be followed up until resolution of the adverse event and standard management should be undertaken.

Revised ACTG Toxicity Grade	Definitions	Investigator Action
Grade 1	Pruritus without rash	May continue therapy
Grade 2	Localized urticaria	May continue therapy
Grade 3	Generalized urticaria Angioedema	Discontinue Therapy
Grade 4	Anaphylaxis	Discontinue Therapy

12.9. Appendix 9: HIV Testing Algorithm and Management of HIV Infection in Study Participants

- HIV testing at Day 1 and the subsequent visits will use POC HIV testing kits in accordance with local standard operating procedures. Additional testing is required for participants who have a reactive or positive HIV test after enrolment. Stored plasma from the visit previous to the positive test should be tested for HIV using the 4th generation HIV test to best estimate time of infection. HIV acquisition must be confirmed by either western blot, HIV ½ Multispot or the Geenius HIV Confirmation ½ Assay, and HIV RNA ([Branson](#), 2014).

[figure not shown]
Reference:

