8. DISCONTINUATION CRITERIA

8.1. Discontinuation of Study Treatment

Participants who discontinue study treatment during the oral phase will be withdrawn from the study. Participants who discontinue treatment during the injection phase should be followed up for at least 56 weeks after their last injection as per the schedule of activities.

[figure not shown]

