8.1.3. Follow up visits for participants withdrawn from IM dosing

Participants that are withdrawn from study treatment will continue to be followed for 56 Weeks. All participants who have received at least 1 injection will be followed as per the follow-up phase of the study. Starting eight weeks post last injection, participants will be seen once every 12 weeks for up to 48 weeks.

At each visit the following long term follow up procedures will be performed:

- HIV POC test
- HIV counselling
- Offer condoms and lubricant
- Adverse event and SAE review
- Concomitant medication review
- Liver function tests
- Plasma sample for drug level
- Plasma sample for storage

Final visit will be performed at 56 weeks post last injection (see Section 2) Week 89.

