8.2. Withdrawal from the Study

8.2.1. Withdrawal from the Study Treatment

A participant may withdraw from the study treatment at any time at his/her own request, or may be withdrawn at any time at the discretion of the Investigator for safety, behavioral or administrative reasons. Participants that are discontinued from treatment during the Oral Phase will end their participation at that time. Participants that are discontinued from treatment during the Injection phase will enter the post treatment period unless consent is withdrawn. All participants who have received at least 1 injection of CAB LA will be followed as per the follow-up phase of the study. Starting eight weeks post last injection, participants will be seen once every 12 weeks for up to 48 weeks. Every effort should be made to complete the early termination study procedures and observations if the participant does not enter post-treatment follow-up.

Any laboratory parameter that meets the stopping criteria should be repeated once to confirm the value prior to withdrawal

Reasons for study treatment discontinuation during the Oral or Injection Phase may include:

- Confirmed HIV acquisition
- Any clinically significant AE deemed to require discontinuation of investigational product
- Grade 3 or higher rash or Grade 2 rash with evidence of systemic involvement
- Grade 2 or higher allergic reaction
- Post entry co-enrolment in an HIV prevention study
- Use of PrEP during the course of the study
- Behaviors assessed by the investigator as being at “high risk” for HIV infection during the course of the study

These thresholds assume that participants are asymptomatic with respect to these changes. In the presence of clinically significant symptoms, lower thresholds for these parameters may need to be used for consideration of possible withdrawal of participants from the study treatment, after consultation between the Principal Investigator and a Medical Monitor.

Before discontinuing a participant from investigational product(s), the Investigator must contact the Medical Monitor. In the event that the investigator is unable to reach the

Medical Monitor, the Investigator, at his or her discretion, may withhold investigational product(s) from a participant until the Medical Monitor or designee can be contacted.

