For participants with Grade ≥ 3 diarrhea that is unresponsive to the recommended dose of the anti-motility agents and for which an alternative etiology (e.g., infectious diarrhea) is not established, the treatment with the anti-motility agent and IP must be interrupted until resolution of diarrhea to Grade ≤ 2 or Baseline, after which IP and background ART may be resumed after discussion and agreement with the Medical Monitor. If Grade ≥ 3 diarrhea recurs within 28 days upon the resumption of IP, the IP should be permanently discontinued and the participant withdrawn from the study.

If loperamide is used for treatment of diarrhea, local prescribing information should be followed with respect to dose and frequency of administration. Loperamide dosing should not exceed local prescribing information.

Hypertriglyceridemia/ Hypercholesterolemia

Samples for lipid measurements must be obtained in a fasted state according to the SoA table (Section 2). Participants who experience asymptomatic triglyceride or cholesterol elevations may continue to receive IP. Clinical management of participants with hypertriglyceridemia/hypercholesterolemia should not be based upon non-fasting samples (obtained in the fed state). A confirmatory fasting triglyceride and/or cholesterol level should be obtained prior to the institution of medical therapy for hyperlipidemia. Isolated Grade 3 and Grade 4 lipid abnormalities do not require withdrawal of IP.

Please see the Recommendations of the Adult AIDS Clinical Trial Group Cardiovascular Disease Focus Group [Dube, 2003] for full discussion of management of hyperlipidemia in the context of HIV therapy.

Decline in Renal Function

Participants who experience an increase in serum creatinine from Baseline of 45 micromoles/liter ($\mu\text{Mol/L}$) (or 0.5 milligrams/deciliter [mg/dL]) should return for a confirmatory assessment within 2 to 4 weeks. A urinalysis and urine albumin/creatinine and urine total protein/albumin ratios should also be done at this confirmatory visit. If the creatinine increase is confirmed, the investigator should contact the study medical monitor to discuss additional follow-up and medical management.

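### In seven toxicity situations, Protocol Appendices 8 and 4 order injected participants out of the trial, although Section 8 and the synopsis require long-term follow-up after the last injection

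*Protocol*

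**What the plan says.** Protocol Appendix 8 (Toxicity Management) contains six orders to leave the trial.

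- Grade 1 anaemia, and separately Grade 2 anaemia, when any of the added haemolysis tests is abnormal: "participants will permanently discontinue study medication and be withdrawn from the trial".
- Grade 3 or 4 anaemia, and separately Grade 3 or 4 bilirubin: "Participants will permanently discontinue study medication and be withdrawn from the trial".
- Grade 3 allergic reaction, and separately Grade 4: "Participants will permanently discontinue the study medication and be withdrawn from the trial".

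Each adds that the participant is followed until the event resolves. Appendix 4 supplies a seventh order, for Grade 3 or higher diarrhoea that recurs after dosing resumes: "the IP should be permanently discontinued and the participant withdrawn from the study".

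The body of the protocol gives a different rule.

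- Section 8.1: "Participants who discontinue treatment during the injection phase should be followed up for at least 56 weeks after their last injection".
- Section 8.1.3: "All participants who have received at least 1 injection will be followed as per the follow-up phase of the study".
- Section 8.2.1: "All participants who have received at least 1 injection of CAB LA will be followed as per the follow-up phase of the study".

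Section 8.2.1 and the synopsis name withdrawal of consent as the exception. The synopsis gives the period as one year.

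Appendix 8 handles rash differently. After drug is stopped for Grade 3 or 4 rash, "The participant should remain on the study to be followed for safety and PK".

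**The concern.** A participant who has been injected and then meets one of the seven triggers is covered by two instructions that disagree. None of the seven is limited to the oral phase.

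What is at stake is the scheduled follow-up. Section 3.3.1 notes that drug can stay in the circulation for months after CAB LA is stopped, and that a man newly infected during that time may develop resistance. It names HIV testing and the 56-week follow-up among the mitigations. Section 8.1.3 specifies an HIV point-of-care test, liver tests and a plasma drug level at each follow-up visit. The appendices' follow-up to resolution specifies no HIV test and no drug level. A site that obeyed them could drop these checks in participants stopped for toxicity.

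A smaller problem sits beside the bilirubin trigger. SAP 7.1.3 grades laboratory results by Protocol Appendix 7, whose Grade 3 and 4 total bilirubin rows require clinical features. Appendix 8 calls the same values Grade 3 or 4 on the number alone.

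**Working it through.** **Count of orders.** Appendix 8: anaemia 3 + bilirubin 1 + allergic reaction 2 = 6. Appendix 4: 1. Total 7.

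**Does leaving the trial just mean stopping drug?** Three places suggest not.

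- Within Appendix 8, Grade 3 and 4 rash stop drug but keep the participant on study, so the appendix separates the two actions.
- Appendix 6 stops study treatment for ALT of 3 times ULN or more without removing the participant from the trial.
- Section 8.2.1 lists allergic reaction of Grade 2 or higher among reasons to stop treatment, which leads to follow-up. Appendix 8 sends Grade 3 and 4 of the same event out of the trial.

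**Oral phase.** There is no conflict: Sections 8.1 and 8.2.1 already end participation for those who stop during oral dosing.

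**The 56 weeks reproduced.** Follow-up starts 8 weeks after the last injection, with visits every 12 weeks for 48 weeks: 8 + 4 × 12 = 56. For a full course the last injection is at Week 33, and 33 + 56 = 89. Visits at Weeks 53, 65, 77 and 89 fall 20, 32, 44 and 56 weeks after that injection.

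**Loss per affected participant**, if the site follows the appendix and stops at resolution:

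- resolved by week 8 after the last injection: 4 visits, 56 − 8 = 48 of 56 weeks (86%);
- by week 20: 3 visits, 36 of 56 (64%);
- by week 32: 2 visits, 24 of 56 (43%);
- by week 44: 1 visit, 12 of 56 (21%).

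Resolution before week 8 loses more than 48 weeks. It also cuts into the primary safety window, which SAP 7.1 runs to 8 weeks after the last injection.

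**How many participants.** The documents give no rate. As an assumption only, a per-participant probability p of 0.5%, 1%, 2.5% or 5% among the planned 40 gives 40p = 0.2, 0.4, 1 or 2 expected cases. The chance of at least one, 1 − (1 − p)^40, is then 18%, 33%, 64% or 87%.

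**Bilirubin.** Read literally, Appendix 7 grades total bilirubin as follows:

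- 1.6 to below 2.6 times ULN is Grade 2;
- 2.6 to below 5.0 is Grade 3 only with clinical signs of liver toxicity;
- 5.0 or more is Grade 4 only with life-threatening consequences.

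So 2.59 is Grade 2, while 2.6, 3, 4.9, 5 and 6 without clinical features have no grade. The effect on the Grade 2 or higher laboratory table (2.16) is at most 1/40 = 2.5 percentage points per such participant in the injection phase and 1/48 = 2.1 in the oral phase. It is zero if he also has a value of 1.6 to below 2.6 in that phase. That is plausible, because Appendix 8 requires repeat tests and SAP 7.1.3 counts unscheduled values toward the maximum grade. The maximum-grade shift in Table 2.22 would still be understated.

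**The case against.** The strongest reply is that the rule is stated often enough to prevent error. Section 8 gives it three times and the synopsis once. The heading of Section 8.2, on withdrawal from the study, leads straight into text about stopping treatment and continuing follow-up, so a site that looks up the procedure finds the right rule. Section 8.2.1 requires contact with the Medical Monitor before drug is stopped. Section 9.4.7 requires clinically significant laboratory abnormalities up to 56 weeks after the last injection to be repeated until they settle, which covers anaemia and bilirubin. All of this stands and makes a lapse less likely. It does not remove the conflict: the monitor holds the same two instructions, and 9.4.7 brings no HIV test or drug level.

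On bilirubin, the values still appear in Tables 2.19 and 2.27 and Listing 25, and a drug stop appears in Table 1.4. An event recorded as an adverse event is summarised with the adverse events. In a single-arm descriptive study this part is minor.

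Four stronger readings are tempting, and the documents do not support them.

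- A reader might take 86% as the worst case. It is one scenario; an allergic reaction that settles within days would cost nearly all 56 weeks.
- A reader might infer that the analyses lose these participants altogether. SAP 7.1 and 10.7.1 keep data collected before withdrawal; only later data go.
- A reader might try to date when drug falls below the protective level and so say which lost visits matter most. The sources differ too much. The simulated medians in Section 5.5 imply half-lives of 3.1 weeks (ln 2 ÷ ln(1.35/1.08)) to 4.5 weeks (7 ln 2 ÷ ln(4/1.35)). The observed 8-weekly data in Table 3, with Cmax treated as the 1-week level, give 5.3 weeks (7 ln 2 ÷ ln(3.55/1.43)) and 6.0 weeks (7 ln 2 ÷ ln(3.33/1.49)).
- Appendix 4 also describes withholding and restarting drug for diarrhoea and renal events, which Section 8.1.2 forbids. A reader might conclude that 8.1.2 should be relaxed. But Section 8.1.4.1 and the synopsis bar restart once stopping criteria are met. Appendix 4's mention of background antiretroviral therapy, in uninfected men, suggests that its text may be the part that does not fit.

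**Conclusion.** The conflict is real for participants with at least one injection, and the appendices should be brought into line with Section 8. The size is per person: four scheduled visits and 48 of 56 weeks if the event resolves by week 8 after the last injection, more if sooner, less if later. This assumes that the site follows the appendix, that follow-up ends at resolution and that the Medical Monitor does not intervene. The number affected is probably small and cannot be derived from the documents. The case for change rests on a resistance safeguard that the protocol itself relies on, and not on any distortion of the primary results. The bilirubin grading gap is a minor secondary point.

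**What to change.** In the six Appendix 8 places and the Appendix 4 diarrhoea sentence, replace the order to leave the trial with: *stop study medication for good; anyone who has had one or more injections moves to the 56-week follow-up phase (Section 8.1.3)*. The rash text already works this way. The cost is an amendment to seven sentences. The visits are already scheduled, so no procedure is added.

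In SAP 7.1.3, state that laboratory total bilirubin is graded on its multiple of ULN alone, using the Appendix 7 numeric bands. Footnote Tables 2.16 and 2.22 to say that this grade may differ from the adverse event grade, and record the change in SAP 2.1. The cost is one sentence and a footnote.

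Leave Section 8.1.2 as it is for now. If the conflict over temporary discontinuation is taken up, first reconcile the Appendix 4 withhold-and-restart text, including its reference to background therapy, with Sections 8.1.2 and 8.1.4.1 and the synopsis.
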